2. OBJECTIVES

The primary objectives of our project are to describe perioperative cognitive trajectories of older patients whose elective noncardiac surgery has been deferred because of the COVID-19 emergency, and explore the intra-individual changes in these trajectories from before to after surgery, through periodic remote self-administered cognitive testing.

In the same study population, we will also have the following secondary objectives:

- to describe the perioperative trajectories in mobility/physical function, depressive symptoms and pain, and explore their association with the trajectories in cognitive performance, before and after surgery;
- to describe the change in activities and participation after the COVID-19 and social distancing started, in our study population, compared to a random sample of community-dwelling persons, 65 years old or older, in order to identify the additional impact of surgery deferral. We will pursue this secondary objective comparing our data with the results of an ongoing cross-sectional survey across community-dwelling older adults living in Greater Hamilton areas.

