3.2 Study population

We expect to include 330 patients aged 65 years or older, scheduled for their noncardiac elective surgery whose surgery has been or will be deferred due to the slowdown of the operating rooms during the COVID-19 emergency at the Hamilton Health Science (HHS), St. Joseph's Healthcare Hamilton (SJHH), Woodstock General Hospital, London Health Sciences

Centre, Kingston General Hospital, Memorial University of Newfoundland, University of Saskatchewan, and University of Alberta.

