3.4.2 Changes in activities and participation since COVID-19 questionnaire

Appendix III shows the questionnaire exploring changes in activities and participation since COVID-19. The questionnaire has been developed in the context of a survey study that is being conducted by investigators at the McMaster Institute for Research on Aging (MIRA) & Labarge Centre for Mobility in Aging (LCMA). In the MIRA/LCMA survey the questionnaire is administered, by telephone, to 500 community-dwelling older adults living in Greater Hamilton area, identified through random sampling based on census. In the Co-TELE-SURGE the questionnaire will be administered by the research personnel only once, i.e. at baseline, to collect data on the change in activities and participation experienced by the subject after the social distancing was imposed to face the COVID-19 pandemic, which, for the participants in our study temporally coincided with the change to their surgical plan.

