change, and 10% an improvement of 0.07). Based on a test of comparison of means in one sample, with an alpha error of 0.05 (2-tailed), and a standard deviation for the OBK score of 0.16,¹³ to enrol 330 subjects will be sufficient to test our hypothesis with 80% of power, even in case of an attrition rate as high as 10%.

Recruiting 330 participants is a feasible goal based on the current status of knowledge about the COVID-19 contingency plan. The lockdown of the operating rooms started in March and will last at least until the end of June, or longer, depending on the participating site. During the lockdown, we expect to be able to enroll at least 120 participants at McMaster sites, and 30-50 participants at each of the other participating sites. Even when the operating rooms will reopen to more elective surgeries in the next months, this will happen slowly, so that we expect a carryover of the lockdown at least until the end of the summer. Moreover, it is projected that, if countries increase their normal surgical volume by 20% post-pandemic, it would take a median 45 weeks to clear the backlog of operations resulting from COVID-19 disruption.²⁰ Therefore should we see a recruitment rate slower than expected, for any reason, we will extend our recruitment period to beyond the summer.

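### Secondary objective: comparison with the Greater Hamilton community survey can describe a difference in reported change, but cannot identify the impact of surgery deferral.

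*Combined protocol and SAP*

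**What the plan says.** The second of the secondary objectives in section 2 is to describe the change in activities and participation since COVID-19 and social distancing began, compared with a random community sample aged 65 or older, "in order to identify the additional impact of surgery deferral". The comparator is "an ongoing cross-sectional survey across community-dwelling older adults living in Greater Hamilton areas". Section 3.4.2 gives its size and sampling: "500 community-dwelling older adults living in Greater Hamilton area, identified through random sampling based on census", interviewed by telephone.

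The cohort is defined differently. Section 3.2 states: "We expect to include 330 patients aged 65 years or older". It lists two Hamilton hospitals and six sites elsewhere: Woodstock, London, Kingston, Newfoundland, Saskatchewan and Alberta. Section 3.5 forecasts at least 120 patients at McMaster sites and "30-50 participants at each of the other participating sites". Section 3.2.1 requires both planned inpatient noncardiac surgery and deferral of it. Section 3.2.2 excludes known dementia, lack of a connected tablet or computer, and inability to understand English.

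The questionnaire (Appendix III) is given once, at the baseline videoconference, and asks how abilities have changed since distancing began. Section 3.4.2 says that for study participants the start of distancing "temporally coincided with the change to their surgical plan". Section 3.2 describes patients "whose surgery has been or will be deferred".

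**The concern.** The objective promises an attribution to deferral. To support it, the comparator would have to resemble the patients in everything that affects reported change except the deferral. A general community sample does not: its members are not selected for a condition that needs surgery, they live in one area, and no cohort-style exclusions are stated for them. The plan has no surgical patients whose operation went ahead on time.

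At stake is the reported conclusion. Several items concern walking, climbing stairs, housework and exercise, which a condition awaiting surgery could itself worsen. A difference between the groups could be published as harm from deferral when illness, region or selection explains some or all of it.

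**Working it through.** **1. What the contrast estimates.** For a patient, write mean reported change as

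D(site) + C + F + S + M

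where D(site) is the effect of distancing and local circumstances at the patient's site, C the course of the surgical condition, F the effect of deferral, S the effect of the eligibility restrictions and M that of interview mode. For the survey, taken as the reference for the other terms, it is D(Hamilton). The difference is

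F + C + [D(site) − D(Hamilton)] + S + M.

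The objective reads this as F. Under inclusion criteria 2 and 3, C and F are both present in every patient, so no subgroup of the cohort and no reweighting to the survey can separate them. This step does not depend on any count.

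**2. Whether an analysis addresses it.** Sections 3.6.1 and 3.6.2 cover the cognitive tasks, physical function and mobility, depressive symptoms and pain. They define no score, contrast, adjustment, standardisation or restriction for this questionnaire.

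**3. Regional mismatch.** Inputs: 330 patients (section 3.2), and at least 120 at McMaster sites and 30 to 50 at each other site (section 3.5). Assumptions: the McMaster sites are the two Hamilton hospitals, and site stands for residence. With the total held at 330:
- McMaster at its floor: (330 − 120)/330 = 210/330 = 64% from elsewhere, or 35 per other site, within the forecast.
- Six other sites at their minimum: 6 × 30 = 180, and 180/330 = 55%.

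If Woodstock were counted as a McMaster site, the five remaining sites at their minimum would give 150/330 = 45%.

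**4. Timing.** Section 3.4.2 treats distancing and deferral as simultaneous. Section 3.2 also admits deferrals still to come, and this protocol version, dated May 31, 2020, already describes distancing as in force. For those patients the recall period may start before the deferral. Their number cannot be derived from the documents.

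**5. Interview mode.** The survey is by telephone; the cohort answers at the baseline videoconference.

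**6. Precision with and without the other sites.** The plan gives no power or precision for this comparison. Its 330 comes from the One-Back hypothesis: (0.16 × 2.80/0.026)² ≈ 297, and 297/0.9 = 330.

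For the proportion reporting a worsening, assumed to be 50%, the 95% half-width is 1.96 × √(0.25/n + 0.25/500):
- n = 330: 0.070, or 7.0 percentage points.
- n = 120: 0.100, or 10.0 percentage points.

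Power for 50% versus 60% (two-sided 0.05, pooled null variance) falls from about 81% to about 51%.

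If a continuous score is assumed instead, the difference detectable with 80% power is 2.80 × √(1/n + 1/500): 0.199 SD at n = 330 and 0.285 SD at n = 120.

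**The case against.** The strongest defence is the questionnaire's format. It asks about change since distancing began, so each respondent is their own reference and some baseline difference in illness and function drops out. That stands. It does not remove worsening of the condition over the same months, or local circumstances that differ between sites.

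It is also fair that this is a secondary objective based on one baseline questionnaire, that the Study Summary does not list it among the secondary objectives, and that its main verb is to describe. The purpose clause nevertheless goes further than description.

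Three stronger readings are tempting, and the documents do not support them:
- A reader might infer that two thirds of the patients live outside Hamilton. The documents give a recruitment forecast by site, not residence, and 120 is a floor. A share of 71% (300/420) would need 420 patients.
- A reader might infer that regional restrictions are known to bias the result. The documents do not describe how restrictions differed between regions, so size and direction are unknown.
- A reader might infer that restricting to Hamilton patients would recover the effect of deferral. It addresses region only; the condition and the deferral remain inseparable. Making that restriction the main analysis is therefore a debatable trade of precision, not a necessity.

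**Conclusion.** The stated purpose does not follow from the comparison, even if the plan is carried out exactly. The decisive reason is that needing surgery and having it deferred coincide in every patient, which rests on the inclusion criteria alone. Region, eligibility restrictions and interview mode are further possible differences. The regional share of about 55% to 64% depends on the recruitment forecast, a total of 330, six sites outside Hamilton, and site as a proxy for residence. The timing inconsistency between sections 3.2 and 3.4.2 is real in logic but cannot be sized.

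The comparison keeps descriptive value. The within-patient cognitive analysis does not use the survey and is unaffected. This should be corrected, but it does not threaten the study's main result.

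**What to change.** - In section 2, replace "in order to identify the additional impact of surgery deferral" with: *to describe the difference in reported change*. State that any difference combines the surgical condition, deferral, region and selection, and will not be attributed to deferral alone.
- In section 3.6.2, add a short analysis for this questionnaire. Standardise the comparison to the survey by age and sex where the survey data allow, and report a Hamilton-sites-only comparison beside the all-site one as a sensitivity analysis for region.
- In section 3.4.2, qualify the statement on timing so that it agrees with section 3.2. A separate analysis of later-deferred patients is not asked for: it needs a deferral date, which section 3.4 and Appendix I do not list.

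The cost is a weaker stated conclusion and lower precision in the Hamilton-only comparison: about 10 rather than 7 percentage points, or about 0.28 rather than 0.20 SD, at about 120 versus 500. Those figures take no account of precision lost to standardisation, and the SD figures need a continuous score that the plan does not define. Standardisation also needs age and sex data from the survey, whereas section 2 promises only its results. No new data from the patients are needed.

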3. METHODS

3.1 Study design

Our project is a multicentre, prospective and longitudinal, cohort study.

3.2 Study population

We expect to include 330 patients aged 65 years or older, scheduled for their noncardiac elective surgery whose surgery has been or will be deferred due to the slowdown of the operating rooms during the COVID-19 emergency at the Hamilton Health Science (HHS), St. Joseph's Healthcare Hamilton (SJHH), Woodstock General Hospital, London Health Sciences

Centre, Kingston General Hospital, Memorial University of Newfoundland, University of Saskatchewan, and University of Alberta.

3.2.1 Inclusion criteria

1. age 65 years or greater
2. patient scheduled to perform noncardiac elective surgery expected to require at least an overnight stay in hospital after surgery
3. surgery deferred, with a known or probable surgery date in ≥6 weeks
4. informed consent provided

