1. BACKGROUND AND RATIONALE

The COVID-19 emergency has been impacting our patients and healthcare systems in several ways. To redeploy resources (staff and equipment) to priority areas, ensure hospital capacity to front the COVID-19 surge, and for infection control reasons, the use of operating rooms have been limited mainly to semi-urgent (e.g., oncology), urgent (e.g., hip fracture) and emergency (e.g., ruptured abdominal aortic aneurysm) surgeries, while many elective surgeries have been deferred to a later, often undermined, time. From a societal perspective, this is certainly thought to be the best choice in such an emergency. From an individual perspective this is going to represent a stressful situation for those patients, often older, whose surgery is not happening as planned.

On the other side, from an epidemiological perspective, this represents a unique opportunity to study the impact of surgery on cognitive performance. Postoperative cognitive dysfunction (POCD) is an objectively measured decline in cognition postoperatively compared with preoperative function.^{1,2} The NeuroVISION study demonstrated that as many as 30% of patients aged 65 or older undergoing elective noncardiac surgery experience cognitive decline at 1 year after surgery, defined as ≥ 2 point decline in the Montreal Cognitive Assessment compared with before surgery.³ This has questioned the role of surgery in cognitive decline. Many of these patients have several comorbidities, which, in addition to age, could theoretically impact their cognitive performance over time. Therefore, it is still uncertain whether the decline we see in these patients who underwent surgery is different from what we would have seen if the same patients had not undergone surgery. An epidemiological study could try to answer this question comparing the surgical cohort with a matched non-surgical cohort. However, whatever matching approach we use, the control group is always going to be imperfect, and undoubtedly inferior to an approach that compares the individual with themselves. However, when we evaluate the effect of surgery comparing the patient cognitive performance at a certain time point after surgery with the cognitive performance measured at only one time point before surgery, we miss considering a possible pre-existing trend over time before surgery, which could hypothetically explain the change after surgery.

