3.2.2 Exclusion criteria

1. patient undergoing cardiac surgery, cranial surgery
2. known history of dementia
3. unavailability of tablet or computer with an internet connection for remote assessment
4. patient unable to interact with a tablet or computer due to language, visual, or hearing impairment, or any severely limited mobility of the upper limb joints
5. patient unable to understand spoken or written English
6. surgery delayed for an intercurrent clinical event

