3.4 Measurements

At the initial videoconference, data on baseline characteristics will be collected, including demographics, social history, comorbidities, and relevant pharmacological and non-pharmacological (e.g. radiation) therapies. At the initial videoconference the questionnaire to explore change in activities and participation since COVID-19 will be also administered.

At each of the calls that will remind the self-administered cognitive assessment, the research team member will also

- 1) ask about any clinically relevant intercurrent event (i.e. hospital admissions, ED visits, visits to urgent care, changes in medications);
- 2) assess mobility/physical function based on the Late Life Function and Disability Instrument: Function Component (LLFDI), and life space mobility questions
- 3) assess depressive symptoms using the Geriatric Depression Scale (GDS)
- 4) assess pain using a Numeric Pain Rating Scale (NPRS)

Data on the participant past medical history, medication, date and type of surgery, postoperative course, and intercurrent clinical events will be obtained from the interview with participant, and confirmed or completed through review of electronic hospital medical records, based on the execution of a Data Transfer Agreement between McMaster University and Hamilton Health Sciences Corporation. If needed, for data completion or clarification, the participant's family physician will be also contacted.

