3.6.1 Primary analysis

We will report descriptive summary statistics of the performance of the study population at each of the 4 CBB tasks for each of the preoperative and postoperative time points. We will also represent individual and averaged performance trajectories graphically.

To explore whether surgery has a statistically significant impact on cognitive performance and its trajectories, we will model data using interrupted time series analyses. Interrupted time series analysis is a powerful quasi-experimental design to study the longitudinal effects of interventions or exposures, accounting for pre-intervention/pre-exposure trends. We will adopt the approach described in Kontopantelis *et al.*, *BMJ* 2015.^{21 22} According to this approach we will use regression models in which the within patient performance variation over time is partitioned into three main components, to provide independent tests for the slope in scores in the pre-operative period (test 1); the change in level (i.e., absolute change) around surgery, allowing for the trend before surgery (test 2); and the change in slope from before to after surgery (test 3).^{21 22} The preoperative slope quantifies the trend in performance before surgery. The level change is an estimate of the absolute change in cognitive performance that can be attributed to surgery, i.e., between the time points immediately before and immediately after surgery, and accounting for the preoperative trend. The change in slope quantifies the difference between the preoperative and postoperative slope. Based on the hypothesis that the postoperative trajectory will not be homogenous over the 12 months after surgery, we will also adopt a more complex interrupted time series model that will allow for different slopes of change in different time segments, i.e. right before to 1 month after surgery, 1-3 months, 3-6 months, and 6-12 months after surgery.²³ We will conduct the primary analysis first considering only the early-intermediate postoperative performance (up to 6 months after surgery). With the assumption that the

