impact of surgery can last as long as one year,² we will repeat the analysis including also the change between 6 and 12 months after surgery. In our regression models, we will use estimates of error variance obtained from bootstrap techniques using 1000 bootstrap samples. We will analyze the performance at each task separately, and then combining the 4 scores into one unique measure of performance. We will explore whether clinically significant changes have occurred at any time point. There is no standard definition for what is a clinically significant perioperative decline across different tests.^{24 25} In addition to the change as defined in our sample size calculation (i.e. a change in score equal to or greater than the average difference in scores between a healthy older adult and a subject with MCI), we will consider also 2 most commonly adopted definitions, i.e. 1) a change of $\geq 20\%$ in test scores,²⁶ and 2) a reliable change index (RCI) of ≥ 1.65 . The RCI is an index commonly used in neuropsychology,²⁷ and also in studies using the CBB,¹³ calculated by dividing the individual's test-retest difference score by the standard error of that difference score, and can be interpreted as a standard Z score. The cut-off of RCI=1.65 is the point beyond which 5% of the values from the normal sample population will fall (i.e. $P<0.05$, one tailed test). We will compare the performance scores at each time point with the preceding time points, and evaluate the changes based upon these criteria. We will provide the number and percentage of patients experiencing a cognitive decline based on these definitions at each of the segments of the observation period. We will also compare our study population data with existing age-stratified normative data for the CBB.²⁸

In our primary analyses, we will include only patients who completed ≥ 2 assessments preoperatively and ≥ 3 assessments (i.e. 1, 3, and 6 months) postoperatively. Secondarily, we will repeat our analysis dealing with missing data 1) through multiple imputation techniques; and 2) using a method of evidence-informed data imputation, previously implemented in our studies, which takes onto account the reason for the missing data.³

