3.6.2 Secondary Analyses

We will explore whether the effect of surgery on cognitive trajectories differ based on baseline patient characteristics, including age, type of surgery, cognitive performance at baseline, comorbidities, mobility, GDS and pain score. This will be done studying the interaction of these covariates with the components of the interrupted time analysis. The interrupted time series approach as described assumes linearity and constancy of the preoperative trend when projected postoperatively. We will evaluate the validity of these assumptions exploring the association of changes in cognitive performance with intercurrent events other than the index surgery, for the long-term effects.

With a similar approach as for the cognitive performance, we will study the perioperative trajectories of patient physical function/mobility (as indicated by the LLFDI-FC and the life space mobility questions), depressive symptoms (as indicated by the GDS), and of pain (as indicated by the NPRS). We will also explore whether the time-dependent LLFDI-FC, GDS and NPRS scores are associated with the time-dependent cognitive scores.

STATA software, version 15, will be used for the analyses.

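### Elective status is fixed only at scheduling, so if a deferred patient is finally operated on urgently, the acute illness enters the level change attributed to surgery

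*Combined protocol and SAP*

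**What the plan says.** Section 3.2.1 requires a "patient scheduled to perform noncardiac elective surgery expected to require at least an overnight stay in hospital after surgery". Section 3.2.2 excludes "surgery delayed for an intercurrent clinical event", which concerns delay and does not address an operation precipitated by an acute event. Section 1 itself separates the deferred elective operations from "urgent (e.g., hip fracture) and emergency (e.g., ruptured abdominal aortic aneurysm) surgeries".

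The primary set in section 3.6.1 is defined by completeness alone: "In our primary analyses, we will include only patients who completed" at least two preoperative assessments and the 1-, 3- and 6-month postoperative ones. The model takes surgery as the interruption, and "The level change is an estimate of the absolute change in cognitive performance that can be attributed to surgery". Section 3.4 lists "date and type of surgery, postoperative course, and intercurrent clinical events" among the data to be collected; urgency is not named there, in the Appendix I row on the index surgery, or among the effect modifiers in section 3.6.2. That section plans to test its trend assumptions by "exploring the association of changes in cognitive performance with intercurrent events other than the index surgery, for the long-term effects". The term index surgery appears in section 3.6.2 and Appendix I without a definition.

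**The concern.** The cohort is selected for waiting. The surgery date must be at least six weeks away, and section 3.5 cites a projected median of 45 weeks to clear the backlog. During the wait the underlying condition can turn acute and the operation be done out of plan.

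The design's strength is that each patient's own preoperative trend stands in for a control group. That works for slow processes already under way before surgery. It does not work for an illness that begins between the last preoperative test and the 1-month test, because that illness coincides with the interruption. Its effect is absorbed into the level change, and a decline caused by acute illness could be read as an effect of elective surgery. If the handling is decided only after the data are seen, the choice is open to the charge of being made on the results.

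**Working it through.** **The plan's own figure.** Section 3.5 gives declines of 0.009 (H0) and 0.035 (H1), so the target is 0.035 − 0.009 = 0.026, with SD 0.16, two-sided alpha 0.05, power 80% and attrition 10%. n = (0.16 × (1.960 + 0.842) / 0.026)² = 297.2, and 297.2 / 0.9 = 330.3. The stated 330 reproduces; there is no arithmetic error here.

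**Shift in the mean.** Shift = share of patients operated on unplanned × their extra decline. Neither input is in the documents. I assume shares of 1%, 5% and 10%, and use the plan's own reference differences as scale: 0.07 (healthy versus MCI) and, as an extreme upper scenario, 0.17 (healthy versus dementia). The last column is the two-sided rejection rate of the section 3.5 one-sample test when elective surgery has no effect: Φ(−1.96 + z) + Φ(−1.96 − z), with z = shift × √297 / 0.16.

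| Share | Extra decline | Shift | Shift / 0.026 | Rejection |
|---|---|---|---|---|
| 1% | 0.07 | 0.0007 | 3% | 5.1% |
| 5% | 0.07 | 0.0035 | 13% | 6.6% |
| 10% | 0.07 | 0.0070 | 27% | 11.7% |
| 5% | 0.17 | 0.0085 | 33% | 15.0% |
| 10% | 0.17 | 0.0170 | 65% | 44.9% |

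**The same shifts in an interrupted time series.** The one-sample test treats the expected decline as known. The planned model estimates the preoperative slope, which costs precision. Assume a within-patient SD of 0.16/√2 = 0.113 (so that a difference of two tests has SD 0.16), independent errors, 297 patients, monthly preoperative tests with the last half a month before surgery, postoperative tests at 1, 3 and 6 months, and an extra decline that persists. The SE unit is 0.113/√297 = 0.00657. The variance multiplier at time t is [1/k + (t − mean)²/Sxx], summed over the preoperative and postoperative lines. The postoperative line has mean 3.33 and Sxx 12.67, giving 1.21 at t = 0 and 0.89 at t = 6.

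- Two preoperative tests (mean −1, Sxx 0.5). Level: 0.00657 × √(2.5 + 1.21) = 0.0127. Six-month departure: 0.00657 × √(98.5 + 0.89) = 0.0655.
- Four preoperative tests (mean −2, Sxx 5). Level: 0.00657 × √(1.05 + 1.21) = 0.0099. Six-month departure: 0.00657 × √(13.05 + 0.89) = 0.0245.

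At a 5% share (shift 0.0035 to 0.0085), rejection for the immediate level change is about 6% to 10% with two tests and 6% to 14% with four. For the 6-month departure it is 5.0% to 5.2% with two and 5.2% to 6.4% with four. At a 10% share and 0.17, the 6-month figure is 6% to 11%, against 44.9% in the table. The 6-month test is little affected because its standard error is large; the point estimate still moves by the full shift if the decline persists.

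**Cost of leaving such patients out.** At 5%, 297 × 0.95 = 282, and power is Φ(0.026 × √282 / 0.16 − 1.96) = 78%. At 10%, 267 patients give 76%.

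**The case against.** The plan never says that an emergency operation is analysed as elective surgery. A reader might infer that from the eligibility wording, but it is an inference from silence. In sections 1 and 2 the word elective describes the population, and the exposure is simply called surgery. Following every deferred patient through whatever operation is received is a legitimate target for a cohort defined at enrolment. This stands: the documents do not show that the plan misstates its own estimand, only that it leaves the matter open.

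The primary set also narrows the group. Patients operated on before a second preoperative test, or too ill to complete the 1-, 3- and 6-month tests, drop out of it. That reduces the share without removing it, and they may return in the imputation analyses.

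Much of the information is collected already. Each call asks about admissions and emergency visits, and hospital records are reviewed, so such cases should usually be identifiable. An emergency visit before the operation could arguably count among "intercurrent events other than the index surgery, for the long-term effects". But that check is secondary, exploratory and aimed at long-term effects, so it leaves the primary level change as it is.

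A reader might also take the one-sample rejection rates, up to 45%, as the false-positive risk of the planned 6-month analysis. They are not: they come from the sample-size test, and the upper end needs both a 10% share and a dementia-sized decline among patients who completed every test.

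**Conclusion.** The gap is real and modest. Any operation serves as the interruption for a patient who meets the assessment counts, and an acute illness that begins with an unplanned operation is then included in the level change attributed to surgery. Neither the preoperative trend nor the section 3.6.2 check takes it out.

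The size cannot be derived from the documents. At an assumed extra decline of 0.07, the shift is negligible at a 1% share (3% of the target) and material at 10% (27%); the 0.17 scenario is an outer bound for illustration. The concern is mainly the immediate level change. The documents do not support reading this as an error in the sample size, as a declared policy of treating emergencies as elective, or as a serious threat to the 6-month test. It is a cheap improvement to make in advance, and recording urgency would show how large the share is.

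**What to change.** - In section 3.4 and the Appendix I row on the index surgery, add a field: performed as the planned elective procedure, or as urgent/emergency. The interview and record review already planned can supply it.
- In section 3.6.1, define index surgery and commit to reporting the number of unplanned operations.
- Prespecify the level-change and 6-month estimates twice, once with all patients and once leaving out those whose operation was unplanned, and state which supports a conclusion about elective surgery.
- Do not fit separate slope terms for the unplanned group if it is small; at shares of 2% to 5% they would rest on about 6 to 15 of 297 patients.

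The cost is one data field and one extra analysis. The elective-only estimate loses a little precision (section 3.5 power about 78% at a 5% share, 76% at 10%) and applies only to patients who reached their operation as planned. No visit or test changes.
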